## **5.2 Summary of the Known Potential Risks and Benefits**

Actinic keratosis is a UV light-induced pre-cancerous lesion of the skin that represents the initial clinical manifestation of intra-epidermal abnormal keratinocyte proliferation. Given the demonstrated potential for progression to SCC, dermatologists generally encourage and actively pursue treatment, with a goal of completely eliminating AK lesions, thereby reducing the risk of progression to invasive SCC.

Data from the two pivotal Phase 3 studies demonstrate that treatment with tirbanibulin ointment 1% once-daily for 5 days is effective in the treatment of AK of the face or balding scalp.

In the pivotal studies, the safety profile of tirbanibulin ointment 1% showed a low rate of treatment-emergent AEs and no unexpected or unanticipated safety findings. The overall incidence of treatment-emergent AEs (TEAEs) was similar between the tirbanibulin ointment 1% and vehicle groups, and there were no treatment-related treatment-emergent serious AEs (TESAEs) or discontinuations due to a TEAE. There were also no long-term safety concerns related to tirbanibulin ointment 1% in patients followed up to 1 year after Day 57.

The most frequently reported local tolerability signs were transient, mild to moderate erythema and flaking/scaling. Treatment-related AEs were mostly transient, mild to moderate application-site pruritus or pain, and most did not require treatment.

The safety profile of tirbanibulin ointment 1% observed in the Phase 1 maximal-use trial M-14687-01, in which study drug was applied to 100 cm^2 on the face or balding scalp, was consistent with that observed in the pivotal studies.

Based on the available efficacy and safety data from the completed clinical and nonclinical studies, the benefit-risk assessment is positive and supports the evaluation of tirbanibulin ointment 1% in this Phase 3 study of patients with AK of the face or scalp.

Further information regarding the nonclinical and clinical characteristics, summaries of the known and potential risks, as well as reasonably expected adverse reactions of the product under investigation, is provided in the Athenex KX2-391 (tirbanibulin) Investigator's Brochure.

### **5.3 Scientific Rationale for the Trial**

Tirbanibulin is an antiproliferative agent that causes cell cycle arrest and apoptosis. In two well-controlled Phase 3 clinical trials, tirbanibulin ointment 1% was demonstrated to be an effective and safe treatment for AK of the face or balding scalp, when applied topically once daily for 5 consecutive days to a field of 25 cm^2 containing 4 to 8 clinically typical, visible, and discrete AK lesions.

On the basis of the Phase 3 trial results, tirbanibulin ointment 1% was approved in the US and Europe for the topical treatment of AK on the face or scalp, over a field up to 25 cm^2. However, AK often affects larger areas of UV light-damaged skin; thus, there is a need for a product to treat AK patients with affected fields larger than 25 cm^2.

This study will assess the safety and tolerability of tirbanibulin ointment 1% administered under the same posology (once daily for 5 days) to a field of approximately 100 cm^2 on the face or balding scalp containing 4 to 12 clinically typical, visible, and discrete AK lesions.

## **6 Objectives and Endpoints**

### **6.1 Objectives**

The primary objective of the trial is to evaluate the safety and tolerability of tirbanibulin ointment 1% when applied to a field of approximately 100 cm^2 on the face or balding scalp.

Additionally, the treatment effect of tirbanibulin ointment 1% when applied to a field of approximately 100 cm^2 on the face or balding scalp will be explored.

### **6.2 Endpoints**

#### **6.2.1 Safety Endpoints**

##### *Safety Endpoints*

- Local Tolerability Assessment:
  - Local tolerability score by visit (0-3) for each individual sign (erythema, flaking/scaling, crusting, swelling, vesiculation/pustulation, and erosion/ulceration)
  - Maximum local tolerability score post baseline through all the visits for each individual sign
  - Time to maximum local tolerability score for each individual sign

- Local tolerability signs composite score (0-18) by visit, defined as the sum of the scores graded from 0 to 3 on all six individual tolerability sign categories
- Maximum local tolerability signs composite score post baseline through all the visits
- Time to maximum local tolerability composite score
- Pigmentation and scarring in the TF through all the visits
- TEAEs, TESAEs, adverse events of special interest (AESIs), clinical laboratory data, and other safety assessments (vital signs, physical examinations [PEs], electrocardiograms [ECGs])

### **6.2.2 Exploratory Endpoints**

- Absolute number, change from baseline, and percent change from baseline in AK lesion count from total lesions in the TF at each visit
- Absolute number, change from baseline, and percent change from baseline in AK lesion count, for lesions that were already present at baseline, from total lesions in the TF at each visit
- Absolute number and percent change of new lesions from total lesions in the TF at each visit

## **7 Trial Design and Rationale**

### **7.1 Trial Design**

This is a Phase 3 multicenter, open-label, single-arm trial to evaluate safety and local tolerability of tirbanibulin ointment 1% administered topically for 5 days over a field of approximately 100 cm^2 on the face or balding scalp in adult patients with AK.

The study consists of a 4-week (28-day) Screening Period, a 5-day Treatment Period, and a Response Assessment Period of approximately 7 weeks (see Table 1, Schedule of Assessments):

- During the Treatment Period, patients will apply tirbanibulin ointment 1% once daily for 5 days beginning on Day 1.
- All patients will be evaluated for safety, tolerability, and the presence of AK lesions in the TF until completion of the Response Assessment Period at Day 57.

### **7.2 Trial Rationale**

#### **7.2.1 Rationale for Trial Design**

Since tirbanibulin ointment 1% is an approved product and there is no change in the formulation or posology, the main objective of this study is to evaluate the safety and tolerability of tirbanibulin ointment 1% applied over an extended field (100 cm^2) in adult patients with AK on the face or balding scalp.

The duration of the study considers both safety and efficacy. From a local tolerability perspective, most of the local signs are expected to be resolved by Day 29. However, the study duration is extended up to Day 57, in order to assess the treatment effect as exploratory endpoints.

In addition to the overall incidence of local tolerability events, the sample size considers detection of local tolerability signs of particular interest, specifically, vesiculation/pustulation and erosion/ulceration (see Section 11.1). When severe, these local tolerability signs can lead to permanent local events such as dyspigmentation or scarring.

### **7.2.2 Rationale for Trial Population**

The study will be conducted in male and female AK patients, aged 18 years or older, having 4 to 12 clinically typical, non-hypertrophic, non-hyperkeratotic, visible, and discrete AK lesions over a field of approximately 100 cm^2 on the face or the balding scalp.

Enrollment will be controlled such that the trial population is representative of the population expected to use the product in terms of age and treated area. A minimum of 50% of patients older than 65 years old will be included and approximately two-thirds of the patients will be treated for AK lesions on the face and one-third on the scalp.

### **7.2.3 Rationale for Trial Dose and Regimen**

In this study patients will be treated with tirbanibulin ointment 1% daily for 5 consecutive days beginning on Day 1. Treatment will be applied to a field measuring approximately 100 cm^2 on the face or balding scalp. There are no changes in treatment duration or posology. Tirbanibulin ointment 1% has shown effectiveness in the treatment of AK lesions and the good safety and tolerability profile supports the field extension to a higher area to satisfy medical needs.

In a Phase 2 trial (KX01-AK-002), efficacy and safety results of 3 and 5-day treatment regimens over 25 cm^2 were compared. The 5-day regimen showed substantial clinical activity and acceptable local tolerability. The 5-day treatment regimen showed a higher proportion of patients with 100% clearance at Day 57 compared with the 3-day regimen (43% vs 32%, respectively), as well as a higher proportion of patients maintaining their treatment response at 12 months (43% vs 30%, respectively). Patients in the 5-day regimen experienced slightly more mild/moderate erythema and flaking/scaling, but local signs were self-limited with both regimens and by Day 29 had essentially returned to baseline values.

### **7.2.4 Rationale for Trial Assessments**

In prior studies, mild to moderate erythema and flaking/scaling were the most frequently observed signs when assessing local tolerability. Local tolerability signs following treatment will be characterized and assessed throughout this study and reported separately from AEs.

Standard safety assessments will be performed throughout the study including the capture of AEs, SAEs, concomitant medications, laboratory testing for hematology, blood chemistry, and urinalysis, PEs and vital signs measures, and ECGs.

Lesion counts in the TF will be performed at Screening, Day 1/Baseline (predose), and at every visit from Day 5 up to Day 57 to evaluate the treatment effect of tirbanibulin ointment 1%, when applied to an area measuring 100 cm^2 on the face or balding scalp.

## 8 Selection of Trial Population and Withdrawal of Patients

### 8.1 Number of Patients

Approximately 125 patients will be screened to initiate treatment in approximately 100 patients.

### 8.2 Inclusion Criteria

All of the following criteria must be met for inclusion of a patient in the trial:

1. Male or female and  $\geq 18$  years old at the time of consent
2. Having a TF on the face or balding scalp (excluding lips, eyelids, and inside nostrils and ears) that
  - measures approximately 100 cm^2 (eg, mid face) and
  - contains 4 to 12 clinically typical, visible, and discrete AK lesions within the TF
3. If a woman of childbearing potential (WOCBP), ie, fertile, defined as a female in the life period from menarche and until becoming post-menopausal (no menses for 12 months without an alternative medical cause) or permanently sterile (with hysterectomy, bilateral salpingectomy, or bilateral oophorectomy at least 3 months prior to Screening), she must:
  - have a negative urine pregnancy test using a highly sensitive method at screening and on Day 1 prior to treatment administration
  - be using highly effective methods of birth control (defined in [Appendix 1](#)) for at least 30 days or 1 menstrual cycle, whichever is longer, prior to the study treatment and must agree to continue use during the study period and until at least 30 days or 1 menstrual period, whichever is longer, after the last dose of investigational product
  - agree to have pregnancy tests while in the study and at the end of the study (according to the Schedule of Assessments in Table 1)
4. Sexually active males with partners who are WOCBP must agree to use two forms of contraception, one of which must be barrier contraception, from Screening through 90 days after their last dose of study treatment. All male patients must agree not to donate sperm or attempt conception from Screening through 90 days following their last dose of study treatment.
5. Willing to avoid excessive sunlight or UV light exposure, including the use of tanning beds, to the face or scalp during the study
6. Ability to understand the purpose and risks of the trial, willingness and ability to comply with the protocol, and provided written informed consent in accordance with institutional and regulatory guidelines

### 8.3 Exclusion Criteria

Patients will be excluded from trial enrollment if they meet any of the following criteria:

1. Presence in the TF of:
  - a) Clinically atypical and/or rapidly changing AK lesions in the TF

- b) Hyperkeratotic or hypertrophic lesions, recalcitrant disease (had cryosurgery on 2 previous occasions) and/or cutaneous horn
- c) Confluent AK lesions (ie, non-discrete lesions defined as per inclusion criteria)
- d) History of invasive SCC, Bowen's disease, basal cell carcinoma (BCC), or other malignant tumors in the TF
- e) Any other dermatological disease that causes difficulty with examination

2. Location of the TF is:

- On any location other than the face or balding scalp
- Within 5 cm of an incompletely healed wound
- Within 5 cm of a suspected BCC or other neoplasia
- Periorbital, lips, or nostrils

3. Previous treatment with tirbanibulin ointment 1%.

4. Anticipated need for inpatient hospitalization or inpatient surgery from Day 1 to Day 57

5. Treatment with 5-fluorouracil, imiquimod, ingenol mebutate, diclofenac, photodynamic therapy, or other treatments for AK within the TF or within 2 cm of the TF, within 8 weeks prior to the Screening visit

6. Use of systemic retinoids (eg, isotretinoin, acitretin, bexarotene) within 6 months prior to the Screening visit

7. Use of the following therapies and/or medications within 4 weeks prior to the Screening visit:

- Cosmetic or therapeutic procedures (eg, use of liquid nitrogen, surgical excision, curettage, dermabrasion, medium or greater depth chemical peel, laser resurfacing) within the TF or within 2 cm of the selected TF
- Treatment with cytotoxic drugs (eg, cyclophosphamide, vinblastine, chlorambucil, methotrexate).
- Treatment with systemic medications that modulate and/or suppress the immune system (eg, cyclosporine, azathioprine, methotrexate, prednisone, alefacept, infliximab, interferons/interferon inducers).
- Therapy/treatment with UV-A or UV-B light.

8. Use of the following therapies and/or medications within 2 weeks prior to the Screening visit:

- Acid-containing therapeutic products (eg, salicylic acid or fruit acids, such as alpha and beta-hydroxyl acids and glycolic acids), topical retinoids, or light chemical peels within the TF or within 2 cm of the selected TF
- Topical steroids within the TF or within 2 cm of the selected TF
- Artificial tanners within the TF or within 5 cm of the selected TF

9. A history of sensitivity and/or allergy to any of the ingredients in the study medication

10. Patients with significant abnormalities on the medical history, PE findings, vital signs, ECG, clinical chemistry, hematology, and urinalysis results that in the judgment of the Investigator may interfere with the interpretation of the results.
11. A skin disease (eg, atopic dermatitis, psoriasis, seborrheic dermatitis, eczema) or condition (eg, scarring, open wounds) that, in the opinion of the Investigator, might interfere with the study conduct or evaluations, or which exposes the patient to unacceptable risk by study participation
12. Significant uncontrolled or unstable medical diseases or conditions that, in the opinion of the Investigator, would expose the patient to unacceptable risk by study participation
13. Females who are pregnant or nursing or seeking to become pregnant
14. Participated in an investigational drug trial during which an investigational study medication was administered within 30 days or 5 half-lives of the investigational product, whichever is longer, before dosing in the current study
15. Patient who is employee or relative to employees at the research site or Almirall

#### **8.4 Treatment Discontinuation Criteria**

Any patient may discontinue from study treatment at any time during the trial at the discretion of the Investigator or at the request of the patient. For patients who discontinue treatment, efforts should be made to encourage the patient to remain in the trial and complete the trial-related assessments. The main reason for such a premature treatment discontinuation must be documented in the electronic case report form (eCRF), as follows:

- Adverse event: If a patient experiences an AE, treatment discontinuation will be at the discretion of either the Investigator or the patient regardless of the causal relationship to the investigational medical product (IMP).
- Protocol deviation: Any protocol deviation detected should be corrected when possible and the patient should be allowed to continue. ONLY the following deviations should lead to treatment discontinuation: those which could affect patient's safety (eg, illness requiring treatment(s) which in the clinical judgement of the Investigator [or after discussion with the trial monitor] might invalidate the trial by interfering with the IMP) or which are due to patient unwillingness to comply with the trial activities or those violations of inclusion and/or exclusion criteria detected
- Lost to follow-up: Non-attendance. In these cases, every effort should be made by the Investigator to ascertain the reason and to assure patient's attendance as soon as possible. Every effort (at least three documented attempts) should be made to contact the patient and documented in the medical records. If patient cannot be reached after that, a registered mail letter will be sent to the patient and documented in the medical records
- Patient's personal request: The patient is permitted to stop his/her treatment at any time during the trial without incurring any loss in his/her medical care. The Investigator should ensure that such discontinuation is not due to an AE or disease exacerbation, in which case the corresponding reason should be recorded
- Pregnancy

## 8.5 Trial Withdrawal Criteria

Any patient may withdraw from the trial at any time during the trial at the discretion of the Investigator or at the request of the patient. The main reason for such a premature study withdrawal must be documented in the eCRF, as follows:

- Adverse event: If a patient experiences an AE, study withdrawal will be at the discretion of either the Investigator or the patient regardless of the causal relationship to the IMP.
- Death
- Protocol deviation: Any protocol deviation detected should be corrected when possible and the patient should be allowed to continue. ONLY the following deviations should lead to patient withdrawal: those which could affect patient's safety (eg, illness requiring treatment(s) which in the clinical judgement of the Investigator [or after discussion with the trial monitor might invalidate the trial by interfering with the IMP] or which are due to patient unwillingness to comply with the trial activities or those violations of inclusion and/or exclusion criteria detected
- Lost to follow-up: Non-attendance. In these cases, every effort should be made by the Investigator to ascertain the reason and to assure patient's attendance as soon as possible. Every effort (at least three documented attempts) should be made to contact the patient and documented in the medical records. If patient cannot be reached after that, a registered mail letter will be sent to the patient and documented in the medical records
- Patient's personal request: The patient is permitted to stop his/her participation at any time during the trial without incurring any loss in his/her medical care. The Investigator should ensure that such withdrawal is not due to an AE or disease exacerbation, in which case the corresponding reason should be selected
- Trial terminated by Sponsor

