## 8.6 Screening Failures

Screen failures are defined as participants who consent to participate in the clinical trial but are not subsequently treated in the study. A minimal set of screen failure information is required to be entered into the database to ensure transparent reporting of screen failure participants to meet the Consolidated Standards of Reporting Trials (CONSORT) publishing requirements and to respond to queries from Competent Authorities. Minimal information includes demography, screen failure reason, eligibility criteria, and any SAE.

Individuals who do not meet the criteria for participation in this trial (screen failures) will not be rescreened.

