## 8.7 Patient Replacement Criteria

Patients who withdraw from the trial at any time will not be replaced.

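### Protocol 8.5 directs withdrawal of dosed patients for uncorrectable deviations that 8.4 uses only to stop treatment; no text says which governs, and a little tolerability data can be lost

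*Protocol*

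**What the plan says.** Protocol 8.4 and 8.5 open their protocol-deviation bullets alike: correct the deviation where possible and let the patient go on. Both then name the same exceptions, namely deviations that could affect safety, unwillingness to comply, and eligibility violations. The consequences differ.

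- Section 8.4: "ONLY the following deviations should lead to treatment discontinuation". For patients who stop treatment, it adds that "efforts should be made to encourage the patient to remain in the trial and complete the trial-related assessments".
- Section 8.5: "ONLY the following deviations should lead to patient withdrawal". The list ends with "or those violations of inclusion and/or exclusion criteria detected", without further qualification.

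Neither section refers to the other, and nothing elsewhere in the protocol or SAP sets precedence.

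Several other provisions bear on the point. Section 8.6 defines screen failures as "participants who consent to participate in the clinical trial but are not subsequently treated in the study", so in practice the eligibility trigger in 8.5 concerns dosed patients. Section 8.7 states that "Patients who withdraw from the trial at any time will not be replaced". Protocol 11.3 and SAP 8 define one population, everyone who received at least one dose. Protocol 11.9 and SAP 7.1 rule out imputation of missing assessments. SAP 14.1 takes each patient's maximum tolerability score from what was observed after baseline.

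**The concern.** The primary objective is safety and tolerability in everyone dosed. Followed as written, 8.5 ends scheduled follow-up of a dosed patient whose eligibility violation is found late and cannot be corrected, even where continued follow-up would harm neither the patient nor the data. There is no per-protocol set that the withdrawal would keep clean.

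The wording is also firmer than for adverse events. Under 8.5, withdrawal after an adverse event is at the discretion of the investigator or patient, whereas the deviation bullet directs it.

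Two things are at stake. If follow-up stops before a sign peaks, the observed maximum can only equal or understate the true one. And because either section can be followed as written, two sites could handle the same deviation differently.

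**Working it through.** The plan gives no count or rate for such withdrawals, so there is no figure on this point to reproduce. The check sets the sections side by side, traces the visit days, and bounds the effect under a stated assumption.

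**1. When each section has effect.** Protocol 9.4 has the fifth dose applied at home before the Day 5 visit. Until then both sections can apply. Afterwards no treatment remains to be stopped, and only 8.5 can change anything.

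**2. Which violations matter.** The safety and unwillingness triggers largely overlap with investigator discretion and patient request, so the practical issue is eligibility. Some criteria in 8.3 bear on safety (9, allergy; 12, unstable disease; 13, pregnancy) or on whether the field can be graded (1e, 10, 11). Others need affect neither: exclusion 3 (prior use of the study drug) and exclusion 15, "Patient who is employee or relative to employees at the research site or Almirall". These two cannot be corrected after dosing.

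**3. What is kept after withdrawal.**
- Data already collected stay in the safety population.
- The ET visit includes the tolerability grading (Table 1).
- Signs, pigment change, scarring or treatment-related AEs open at ET bring the patient back every 7 to 28 days (Protocol 10.5.1.1, 10.5.2.1, 10.5.2.2).
- ET and return gradings are mapped to analysis windows (SAP 7.3, 7.4).
- AEs the patient reports within 30 days of last contact are captured (Protocol 10.7.3).

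**4. The Day 8 window.** Protocol 5.1.5 places the peak of the composite score around Day 7 to 8 in the earlier 100 cm² trial. The SAP windows are Day 8 [6; 11], Day 15 [12; 22] and Day 29 [23; 43].

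- ET on Day 5: the first return is between Day 5 + 7 = 12 and Day 5 + 28 = 33. Of these 22 days, 11 (12 to 22) map to Day 15, 11 (23 to 33) map to Day 29, and none maps to Day 8.
- ET on Day 2, 3 or 4: the earliest return is Day 9, 10 or 11, which can still fill the Day 8 window.
- ET on Days 6 to 11: the ET visit itself falls in the Day 8 window.

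**5. Nothing open at ET.** There are five scheduled post-baseline gradings (Days 5, 8, 15, 29, 57). ET on Day 5 leaves 1 of 5. ET at the Day 8 visit leaves 2 of 5 and keeps the peak.

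**6. Time to maximum.** SAP 14.1 counts days from first dose and censors only patients whose score stays at 0. If Day 5 is the last grading and shows a mild sign, the maximum is recorded as reached at 5 − 1 = 4 days.

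**7. Size.** Assume k = 1 to 5 such patients per 100, all with ET on Day 5, the Protocol 11.1 rates applying to them, and every event first appearing later and missed at any return visit. Expected unrecorded patients = k × rate:

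- vesiculation/pustulation, 8%: 1 × 0.08 = 0.08 to 5 × 0.08 = 0.40
- erosion/ulceration, 12%: 1 × 0.12 = 0.12 to 5 × 0.12 = 0.60

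In the maximum-score table, the expected erosion/ulceration percentage becomes 12% × (100 − k)/100 = 11.88% (k = 1) to 11.40% (k = 5). These are expected values under the assumptions, not a floor on what could be observed.

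**The case against.** The strongest reply is that the sections can be read together: 8.4 governs dosing, 8.5 governs participation, the default in both is to correct and continue, and the retention sentence in 8.4 covers anyone who stops treatment. That is a sensible reading, but no text says it prevails over the directive in 8.5, and it gives no guidance once dosing is over.

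Other objections stand and limit the point.

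- **The trigger should be rare.** Eligibility is checked at Screening and again before dosing on Day 1 (Table 1), and Protocol 9.4 starts treatment only after eligibility is confirmed. Only a violation missed twice matters.
- **Withdrawal is not always pointless.** A reader might infer that it never serves a purpose. Exclusions 1e, 10 and 11 concern examination or interpretation, so ending assessments in those patients spares some gradings that would be hard to attribute.
- **Later signs are not always missed.** A reader might infer that anything first appearing after ET goes ungraded. About 90% of patients are expected to have at least one sign (Protocol 11.1). A patient already returning for another open finding can have a new sign graded then.
- **Large shifts are not supported.** Dropping 5 patients who all had erosion/ulceration would move 12% to (12 − 5)/(100 − 5) = 7.4%, but nothing suggests that withdrawals for deviations would concentrate in patients with signs.
- **A loss of precision is not shown.** The exact 95% interval width at 12% goes from 13.7 points (n = 100) to 14.0 (n = 95) only if five patients contribute nothing. Here their Day 5 grading still enters the maximum, and SAP Appendix 1 makes the population the default denominator.
- **The loss would be visible.** SAP 9.1 tabulates reasons for discontinuation and SAP 9.2 lists all deviations. That sites did differ in handling is conjecture.

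**Conclusion.** The conflict is real and the rule as written gives a slightly worse result than its alternative. For a dosed patient whose violation affects neither safety nor grading, 8.5 ends follow-up of the primary tolerability outcome without protecting any analysis.

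Three things can be lost: an assessment near the peak when ET falls on Day 5; grading of signs, scarring or pigment change that first appear after ET in a patient with no other reason to return; and later scheduled lesion counts, which are exploratory.

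The effect is small. Under the assumed 1 to 5 patients per 100, at most about 0.12 to 0.60 expected patients with erosion/ulceration go unrecorded. That range rests on an assumed count, on the planning rates, and on the worst timing. SAP 6.2 plans no statistical inference, so no decision threshold is affected. This is an optional, cheap improvement and does not threaten the trial's conclusions.

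**What to change.** Add one sentence to 8.5: for patients who have received at least one dose, an eligibility violation or other protocol deviation is not by itself a reason to end follow-up; any remaining treatment is stopped under 8.4, scheduled assessments continue to Day 57 if the patient agrees, and the deviation is recorded for reporting under SAP 9.2. Keep adverse event, investigator discretion for safety, patient request (which covers unwillingness), loss to follow-up, death and sponsor termination as grounds for withdrawal.

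No new procedures are needed, because the visits are already scheduled. The cost is an amendment, which may count as substantial under Protocol 17.3 and so need IRB approval. A few patients with deviations, some with gradings that are harder to interpret, would also stay in the by-visit tables. They are already in the safety population, and their deviations are listed. If follow-up has already ended, the sentence is for the next protocol.
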